Appendix Table 2. Literature References for Historical Control Rate Calculations in Korea

SVR Rates in Korea			
Population	SVR%	SVR n/N	Reference
GT-1 Treatment Naïve (Peg-IFN/RBV 48 Weeks)	80.8	21/26	{24236}
	54.7	58/106	{24236}
	62.7	341/543	{26807}
	62.2	158/254	{26389}
	64.2	104/162	{26389}
	66.0	31/47	{26390}
Overall SVR Rate	62.7%		
SVR Rates in Korea Elderly			
Population	SVR%	SVR n/N	Reference
GT-1 Treatment Naïve (Peg-IFN/RBV 48 weeks)	30.8	4/13	{26390}
Overall SVR Rate	30.8%		
SVR Rates in Korea Cirrhotics			
Population	SVR%	SVR n/N	Reference
GT-1 Treatment Naïve (Peg-IFN/RBV 48 weeks)	24.0	12/50	{24405}
Overall SVR Rate	24.0%		

Appendix Table 3. Literature References for Historical Control Rate Calculations in China

SVR Rates in China			
Population	SVR %	SVR n/N	Reference
GT-1 Treatment Naïve (Peg-IFN/RBV 48 weeks)	70.3	102/145	{24797}
	43.9	18/41	{13261}
	46.0	58/126	{24391}
Overall SVR Rate	(102+18+58) / (145+41+126) = 57%

E _{max}	maximal effect
EOT	End of Treatment
FDC	fixed-dose combination
FU	follow-up
HCV	hepatitis C virus
HLT	high level term
HLGT	high level group term
HRQoL	Health-Related Quality of Life
H0	null hypothesis
H1	alternative hypothesis
IFN	interferon
INR	International Normalized Ratio of prothrombin time
IVRS	Interactive Voice Response System
LDV	Ledipasvir

LLT	lower level term
LLOQ	lower limit of quantitation
MedDRA	Medical Dictionary for Regulatory Activities
PG	Pharmacogenomics
PK	pharmacokinetics
PT	preferred term
Q1	first quartile
Q3	third quartile
RBV	ribavirin
RNA	ribonucleic acid
SAE	serious adverse event
SAP	statistical analysis plan
SOC	system organ class
SOF	sofosbuvir
SVR	sustained virologic response
SVRx	sustained virologic response x weeks after stopping study drug
TE	treatment-emergent
TFLs	tables, figures, and listings
ULN	upper limit of normal
VF	virologic failure
WHO	World Health Organization

1. INTRODUCTION

This statistical analysis plan (SAP) describes the statistical analysis methods and data presentations to be used in the summary and analysis of data from Study GS-US-337-0131 for Mainland China (hereafter referred to as China), and for the study Overall, i.e., China plus other regions of Korea and Taiwan. This SAP was based on the protocol amendment 3.0 12 February 2016. Related documents are the original study protocol, protocol amendments, and electronic case report form (eCRF). Any changes made after the finalization of the SAP will be documented in the clinical study report (CSR). Analysis of data for subjects enrolled in Korea and Taiwan has previously been conducted in accordance with the SAP dated 22 July 2014 and reported in an interim CSR dated 10 October 2014.

1.1. Study Objectives

1.1.1. Primary Study Objectives

- To determine the antiviral efficacy of treatment with ledipasvir (LDV)/sofosbuvir (SOF) fixed-dose combination (FDC) as measured by the proportion of subjects with sustained virologic response (SVR) 12 weeks after discontinuation of therapy (SVR12, defined as HCV RNA < lower limit of quantification [LLOQ] 12 weeks post treatment)
- To evaluate the safety and tolerability of LDV/SOF FDC as assessed by review of the accumulated safety data

1.1.2. Secondary Study Objectives

- To determine the proportion of subjects who attain SVR at 4 and 24 weeks after discontinuation of therapy (SVR4 and SVR24)
- To evaluate the kinetics of circulating HCV RNA during treatment and after treatment discontinuation
- To evaluate the emergence of viral resistance to SOF and LDV during treatment and after treatment discontinuation

1.1.3. Exploratory Study Objectives

PPD

[Redacted]

[Redacted]

1.2. Study Design

1.2.1. Design Configuration, Subject Population and Treatment Groups

This is an international (China, Korea and Taiwan), multicenter, open-label study in treatment-naïve and treatment experienced adults with chronic genotype 1 HCV infection.

Approximately 180 treatment-naïve and 180 treatment experienced subjects will receive treatment with LDV/SOF 90/400 mg fixed dose combination (FDC) tablet for 12 weeks.

Approximately 200 subjects will be enrolled in China, 80 subjects will be enrolled in Korea, and 80 subjects in Taiwan. Within each country/region approximately 50% (i.e., n~100 or 40) of subjects will be treatment-naïve and 50% will be treatment experienced (i.e., n~100 or 40).

Treatment naïve is defined as having never received treatment for HCV with any interferon (IFN), ribavirin (RBV), or other approved or experimental HCV-specific direct acting antivirals.

Treatment experienced is defined as:

A) IFN intolerant

Note: Subjects intolerant of Peg-IFN α + RBV + HCV protease inhibitor regimens are included in this category.

B) Non-response

C) Relapse/Breakthrough

Note: For treatment experienced subjects, prior exposure to HCV NS3/NS4A protease inhibitors is permitted.

Up to 20% of subjects enrolled in the study may have compensated cirrhosis at Screening.

1.2.2. Study Duration

The total time to complete all study visits is approximately 40 to 42 weeks including:

- 28 to 42 day (4 to 6 weeks) screening period
- 12 week treatment period
- 24 week post-treatment period

1.2.3. Schedule of Assessments

The schedule of assessments is provided as an appendix to the SAP (Appendix 2).

1.3. Sample Size and Power

1.3.1. Treatment Naïve Subjects:

A sample size of 100 Chinese subjects in the treatment naïve group will provide at least 90% power to detect a 17% improvement in SVR12 rate from the historical control rate of 57% using 2-sided exact one-sample binomial test at significant level of 0.05. With 100 subjects in China, the two-sided 95% exact confidence interval for the SVR12 rate will extend at most 20% in length.

1.3.2. Treatment Experienced Subjects:

For treatment experienced subjects, a confidence interval approach will be used to justify the sample size given that our goal is to characterize the SVR rate in a population with limited treatment options and not to test a specific hypothesis. With 100 subjects in China, the two-sided 95% exact confidence interval for the SVR12 rate will extend at most 20% in length.

2. TYPE OF PLANNED ANALYSIS

2.1. Posttreatment Week 4 Analysis

A posttreatment Week 4 analysis will be conducted for administrative purposes when all subjects in China have completed the posttreatment Week 4 visit or have prematurely discontinued from the study. All efficacy and safety data through the posttreatment Week 4 visit will be included (SVR12 data will not be evaluated at this time). The results will be restricted to a limited group of individuals within Gilead. There will be no changes to the study design or study conduct as a result of this administrative analysis (eg, the analysis would not lead to early termination of the study, and there would be no early stopping, no potential for sample size adjustment, and no changes in the design of the study). This analysis is for evaluation of safety and to facilitate development of the clinical study report.

2.2. Primary Efficacy Endpoint Analysis

The primary efficacy endpoint analysis (for SVR12) will be conducted when all subjects enrolled in China have completed the 12 week post treatment visit or prematurely discontinue from study, and all the safety and efficacy data through the Posttreatment Week 12 visit will be finalized and included in the analysis.

2.3. Final Analysis

The final analysis will be conducted when all subjects enrolled in China have completed the 24 week post treatment visit or prematurely discontinue from study. The data will be finalized after all data queries are resolved for study visits through completion of the 24-week posttreatment visit. At the conclusion of data finalization, the study statistician and statistical programmers will run the final version of tables, figures and listings (TFLs).

3. GENERAL CONSIDERATIONS FOR DATA ANALYSES

3.1. Analysis Sets

Analysis sets define which subjects are included in an analysis. A summary of the number and percentage of subjects in each analysis set will be provided for China and Overall (i.e., China plus Korea plus Taiwan) as part of the subject disposition summary.

3.1.1. Enrolled Analysis Set

The enrolled analysis set includes subjects who were enrolled into the study.

3.1.2. Full Analysis Set

The full analysis set (FAS) includes subjects who were enrolled and received at least 1 dose of study drug, and have chronic genotype 1 HCV infection.

The study drug in this study is LDV/SOF.

3.1.3. Safety Analysis Set

The safety analysis set includes subjects who were enrolled and received at least 1 dose of study drug.

3.1.4. Pharmacokinetic Analysis Set

The PK analysis set will include all enrolled subjects who received at least 1 dose of study drug, and for whom at least 1 population PK parameter can be derived for LDV, SOF or its metabolites (as appropriate).

The PK analysis set will be used for the analyses related to the population PK parameters.

3.2. Subject Groups

Subjects will be grouped for analyses according to prior treatment experience (treatment naïve or treatment experienced) for efficacy analysis using the FAS.

3.3. Strata and Covariates

Not Applicable.

3.4. Examination of Subject Subsets

In addition to analyzing by groups according to prior treatment experience, the primary efficacy endpoint, SVR12, will be analyzed for the following subsets:

- age group on date of first dose of study drug (< 65 years, ≥ 65 years)
- sex (male, female)
- baseline BMI (< 25 kg/m², ≥ 25 kg/m²)
- cirrhosis (cirrhosis, absence of cirrhosis)
- response to prior HCV treatment (nonresponse, relapse/breakthrough, IFN intolerant) for treatment experienced subjects
- IFN eligibility (IFN eligible, IFN ineligible, IFN unwilling) for treatment naive subjects
- baseline HCV RNA (< 800,000 IU/mL, ≥ 800,000 IU/mL) and (< 5 log₁₀ IU/mL, ≥ 5 log₁₀ IU/mL)
- baseline ALT (≤ 1.5 × ULN, > 1.5 × ULN)
- IL28B (CC, Non-CC (CT, TT))
- adherence to study drug (<80%, ≥ 80%)

3.5. Data Handling Conventions and Transformations

The COBAS[®] Taqman[®] HCV Test v2.0 for use with the High Pure System assay was used to determine HCV RNA results of Korea and Taiwan in this study. The lower limit of quantitation (LLOQ) of the assay is 25 IU/mL. Quantitative HCV RNA data for Korea and Taiwan were reported in the CSR dated 10 October 2014 and the synoptic CSR dated 26 February 2015.

The COBAS[®] AmpliPrep/COBAS[®] TaqMan[®] HCV Test v2.0 is used to determine HCV RNA results of China in this study. The lower limit of quantitation (LLOQ) of the assay is 15 IU/mL.

When the calculated HCV RNA value is within the linear range of the assay, then the result will be reported as the “<< numeric value >> IU/mL”. This result will be referred to in this document as the numeric result or as “≥ LLOQ detected” for categorical result.

When HCV RNA is not detected, the result is reported as “No HCV RNA detected” or “target not detected”. This result will be referred to in this document as “< LLOQ target not detected” or “< LLOQ TND”.

When the HCV RNA IU/mL is detected but less than LLOQ of the assay, the result is reported as “< 15 IU/mL HCV RNA detected” for China subjects and “<25 IU/mL HCV RNA detected” for Korean/Taiwan subjects. These results will be referred to in this document as “< LLOQ detected”.

Numerical HCV RNA data with values below LLOQ will be set to the LLOQ minus 1 (ie, 14 IU/mL for China subjects and 24 IU/mL for Korean/Taiwan subjects). HCV RNA values returned as “target not detected” will also be set to 14 IU/mL or 24 IU/mL for China and Korean/Taiwan subjects, respectively.

For selected analyses, HCV RNA data (IU/mL) will be transformed to the logarithmic (base 10) scale (\log_{10} IU/mL).

HCV RNA data for China will be summarized. No analysis of quantitative HCV RNA data for Overall (China plus Korea plus Taiwan) will be conducted.

Categorical data (HCV RNA < LLOQ or \geq LLOQ for China and for Korea and Taiwan) will be summarized for China and Overall (China plus Korea plus Taiwan) regardless of the LLOQs.

Total bilirubin values entered as < 0.2 mg/dL will be analyzed as 0.1 mg/dL; direct bilirubin values entered as < 0.1 mg/dL will be analyzed as 0.05 mg/dL {Nehls 1973}. In general, other than the above 2 exceptions, laboratory data that are continuous in nature but are less than the lower limit of quantitation or above the upper limit of quantitation will be imputed to the value of the lower or upper limit minus or plus 1 significant digit, respectively (eg, if the result of a continuous laboratory test is < 20, a value of 19 will be assigned).

Exposure parameters that are selected for statistical analysis will be natural log-transformed.

Concentration values that are BLQ will be excluded for any ratio or natural log-transformed statistical analysis.

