3.6. Missing Data and Outliers

3.6.1. Missing Data

A missing data point for a given study visit may be due to any one of the following reasons:

- A visit occurred but data were not collected or were unusable
- A visit did not occur
- A subject permanently discontinued from the study before reaching the window

For analyses of categorical HCV RNA data, if a data point is missing and is preceded and followed in time by values that are “< LLOQ TND”, then the missing data point will be set to “< LLOQ TND”. If a data point is missing and preceded and followed by values that are “< LLOQ detected”, or preceded by “< LLOQ detected” and followed by “< LLOQ TND”, or

preceded by “< LLOQ TND” and followed by “< LLOQ detected”, then the missing value will be set to “< LLOQ detected”; otherwise the data point will be termed a failure (ie, \geq LLOQ detected).

Subjects with missing data due to premature discontinuation of the study will have missing data imputed up to the time of their last dose (for on-treatment displays). If study days associated with the last dosing date is greater than or equal to the lower bound of a visit window, and the value at the visit is missing, then the value will be imputed. If the study days associated with the last dosing date is less than the lower bound of a visit window then the on-treatment value at that visit will remain missing.

If no HCV RNA values are obtained after the last dose of any study drug, the subject will be considered a treatment failure for SVR endpoints. However, success for SVR12 who have no further HCV RNA measurements collected will be counted as a success for SVR24 due to the high correlation between these 2 endpoints {Chen 2013}.

For the analyses of continuous HCV RNA efficacy data for China, any subject with a missing value in a visit window that is bracketed by prior and subsequent values of “< LLOQ TND” will be set to “< LLOQ TND” (ie, 14 IU/mL). Subjects with a missing data point preceded and followed by values that are “< LLOQ detected”, preceded by “< LLOQ detected” and followed by “< LLOQ TND”, or preceded by “< LLOQ TND” and followed by “< LLOQ detected” will be set to “< LLOQ detected” (ie, 14 IU/mL). No other imputation will be performed for continuous data. No Overall analysis of continuous HCV RNA data will be conducted.

For health-related quality of life data (ie, SF-36), missing data will not be imputed.

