6. EFFICACY ANALYSES

6.1. Primary Efficacy Endpoint

6.1.1. Definition of the Primary Efficacy Endpoint

The primary efficacy endpoint is SVR 12 (HCV RNA < LLOQ 12 weeks after discontinuation of all study drugs) in the FAS population. The COBAS[®] AmpliPrep/COBAS[®] TaqMan[®] HCV Test v2.0 will be used to determine HCV RNA results of China in this study. The LLOQ of the assay is 15 IU/mL.

The COBAS[®] Taqman[®] HCV Test v2.0 for use with the High Pure System was used to measure HCV RNA of Korea and Taiwan. The LLOQ of the assay was 25 IU/mL.

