6.1.2. Primary Analysis of the Primary Efficacy Endpoint

The primary efficacy analysis described below will compare the observed SVR12 rate for the investigational regimen (i.e., LDV/SOF FDC for 12 weeks) versus the adjusted historical SVR null rate in treatment-naïve, Chinese subjects only.

In addition, a point estimate with a two-sided 95% exact confidence interval using the binomial distribution (Clopper-Pearson method {Clopper 1934}) will be constructed for the SVR12 rate by prior treatment experience for China and Overall (i.e., Korea, Taiwan and China).

Treatment Naïve Subjects

In the primary efficacy analysis the SVR12 rate from China will be compared to the adjusted historical SVR null rate of 57% (as calculated in Appendix 3) using a two-sided exact one-sample binomial test.

The hypothesis for superiority in China is:

H0: SVR12 rate = 57%,

H1: SVR12 rate \neq 57%.

Treatment Experienced Subjects:

There is no treatment option available in China, Korea or Taiwan for treatment experienced patients with GT-1 infection. In the absence of effective antiviral therapy, spontaneous clearance of the HCV is rare. Consequently a nominal SVR rate of 5% is assumed for treatment-experienced subjects.

No statistical hypothesis testing will be performed in treatment experienced subjects. For China and Overall (i.e., China plus Korea plus Taiwan), a point-estimate with two-sided 95% exact confidence interval using the binomial distribution (Clopper-Pearson method) will be constructed for the SVR12 rate.

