6.2. Secondary Efficacy Endpoints

6.2.1. Definition of Secondary Efficacy Endpoints

Secondary efficacy endpoints include the following:

- The proportion of subjects who attain SVR at 4 and 24 weeks after stopping therapy, defined as HCV RNA < LLOQ 4 and 24 weeks after stopping treatment (SVR 4 and SVR 24)
- The proportion of subjects with HCV RNA below LLOQ by study visit
- HCV RNA (\log_{10} IU/mL) and change from baseline in HCV RNA (\log_{10} IU/mL) through Week 12 for China only
- The proportion of subjects with virologic failure as the following:
 - On-treatment virologic failure
 - 1) HCV RNA \geq LLOQ after having previously had HCV RNA < LLOQ, while on treatment, confirmed with 2 consecutive values (note: second confirmation value can be posttreatment), or last available on-treatment measurement with no subsequent follow up values (ie breakthrough)
 - 2) $> 1 \log_{10}$ IU/mL increase in HCV RNA from nadir while on treatment, confirmed with 2 consecutive values (note: second confirmation value can be posttreatment), or last available on-treatment measurement with no subsequent follow up values (ie rebound)
 - 3) HCV RNA persistently \geq LLOQ through 8 weeks of treatment (ie. nonresponse)
 - Relapse
 - 1) HCV RNA \geq LLOQ during the posttreatment period having achieved HCV RNA < LLOQ at end of treatment, confirmed with 2 consecutive values or last available posttreatment measurement
- Characterization of HCV drug resistance substitutions at baseline, during, and after therapy with LDV/SOF

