6.2.2. Analysis Methods for Secondary Efficacy Endpoints

For analyses of HCV RNA < LLOQ by visit while on treatment and during the post-treatment (SVR) follow-up period, subjects will be assigned a value at each visit based on the categorical imputation rules described in Section 3.5. The 2-sided 95% exact confidence interval based on Clopper-Pearson exact method will be provided for the proportion by prior treatment experience for China and Overall {Clopper 1934}. The “HCV RNA < LLOQ” category will be split into the following 2 subcategories: “< LLOQ TND” for subjects with target not detected and “< LLOQ detected” for subjects with < LLOQ in tabular displays.

Graphs for the proportion of subjects with HCV RNA < LLOQ over time during treatment will be displayed.

Summary statistics will be presented for absolute values and change from baseline in HCV RNA (\log_{10} IU/mL) by visit and by prior treatment experience through Week 12 in China. Since LLOQ is 15 IU/mL of COBAS[®] AmpliPrep/COBAS[®] TaqMan[®] HCV Test v2.0 used to determine HCV RNA results of China, while LLOQ is 25 IU/mL of the COBAS[®] Taqman[®] HCV Test v2.0 for use with the High Pure System used in Korea and Taiwan, summary statistics for absolute values and change from baseline in HCV RNA for Overall (ie, China, Korea, plus Taiwan) will not be provided. Results for Korea and for Taiwan using the LLOQ of 25 IU/mL have been reported separately in the GS-US-337-0131 interim CSR dated 10 October 2014. Imputation rules described in Section 3.5 will be used to assign HCV RNA values for missing values at a visit that are bracketed by “< LLOQ TND” and/or “< LLOQ detected”. Otherwise, a missing = excluded analysis will be performed. Plots of the mean \pm SD and median (Q1, Q3) of absolute values and changes from baseline in HCV RNA through Week 12 for subjects in China will be presented.

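### Do the Overall response proportions need a sensitivity table because China is cut at 15 IU/mL and Korea and Taiwan at 25 IU/mL?

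*SAP*

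**What the plan says.** SAP 3.5 and 6.1.1 name two assays. Chinese samples are measured with the AmpliPrep version, LLOQ 15 IU/mL. For the High Pure version used in Korea and Taiwan, SAP 6.1.1 states: "The LLOQ of the assay was 25 IU/mL". SAP 3.5 reports a number "When the calculated HCV RNA value is within the linear range of the assay", and such a result is categorised as at or above LLOQ. Below that, the result is recorded only as detected below 15 (China), detected below 25 (Korea, Taiwan), or target not detected.

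The two kinds of summary are then treated differently:

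- **Quantitative HCV RNA.** SAP 6.2.2 cites the two LLOQs and concludes that "summary statistics for absolute values and change from baseline in HCV RNA for Overall (ie, China, Korea, plus Taiwan) will not be provided".
- **Categories.** SAP 3.5 says that results below, or at or above, LLOQ "will be summarized for China and Overall (China plus Korea plus Taiwan) regardless of the LLOQs". SAP 6.1.2 gives SVR12 with exact intervals for China and for Overall, SAP 6.1.3 does the same by subgroup, and SAP 6.2.2 does so for the by-visit and post-treatment proportions. In the tables, the below-LLOQ "category will be split into the following 2 subcategories": target not detected, and detected.

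Protocol 3.1 defines SVR12 as HCV RNA below LLOQ 12 weeks after stopping therapy. Protocol 6.6.1 permits either assay.

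**The concern.** A Chinese subject with 20 IU/mL is a failure. A Korean subject with 20 IU/mL is a response. Both enter the same Overall percentage. The SAP regards the LLOQ difference as serious enough to drop the Overall means, yet it keeps Overall proportions that are defined by the LLOQ itself and plans no table showing the effect.

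Other rules could extend the effect. SAP 6.2.1 counts relapse when a post-treatment value at or above LLOQ is "confirmed with 2 consecutive values or last available posttreatment measurement", so one Chinese value of 15 to 24 could be enough. Under SAP 3.6.1 such a value next to a missing visit also stops that visit being filled in as below LLOQ, and the missing visit becomes a failure.

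The outputs affected would be the Overall columns for SVR12 (Table 8.1), SVR12 by subgroup (Table 8.2, Figure 2), on-treatment proportions (Table 11, Figure 3), SVR4, SVR12 and SVR24 by visit (Table 12), the SVR12/SVR24 concordance (Table 9), and virologic outcome (Table 10) if shown for Overall. At stake is whether those rates mean what a reader takes them to mean.

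**Working it through.** **Inputs.** LLOQ 15 and 25 IU/mL (SAP 3.5, 6.1.1). Planned numbers per treatment-history group: China 100, Korea 40, Taiwan 40, so Overall 180 (SAP 1.2.1). Null 57%, alternative 57% + 17% = 74%, n = 100, two-sided 0.05 (SAP 1.3.1). The number of Chinese subjects with 15 to 24 IU/mL is not in the documents; call it *a*.

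**1. The plan's own figure.** With equal tails, the exact binomial test at n = 100 rejects 57% at 68 or more responders, or at 46 or fewer. The attained two-sided level is 0.033 and the power at 74% is 92.8%, which agrees with the stated 90% or more. All 100 subjects are on one assay, so pooling does not enter the test. Its effect there is zero.

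**2. Shift against a common 25 IU/mL limit.** Leaving aside missing visits next to a band value, which step 4 covers:

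Overall at common 25 = planned Overall + *a*/180.

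Each subject adds 1/180 = 0.56 points to Overall and would add 1/100 = 1.0 point to China. For SVR12, taking *a* = 0 to 3 as an assumption:

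| *a* | All others respond | Exact 95% lower limit | About 94% at common 25 | Exact 95% lower limit |
|---|---|---|---|---|
| 0 | 180/180 = 100% | 98.0% | 169/180 = 93.9% | 89.3% |
| 1 | 179/180 = 99.4% | 96.9% | 168/180 = 93.3% | 88.6% |
| 2 | 178/180 = 98.9% | 96.0% | 167/180 = 92.8% | 88.0% |
| 3 | 177/180 = 98.3% | 95.2% | 166/180 = 92.2% | 87.3% |

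The 94% comes from the treatment-experienced study in Protocol 1.3 (102/109 = 93.6%). The Japanese study of the same regimen had 171/171 (Protocol 1.2.2.3), nearer the left-hand columns. Three subjects move the rate by 3/180 = 1.7 points; the interval around 169/180 (89.3% to 96.9%) is 7.6 points wide.

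**3. Shift against a common 15 IU/mL limit.** With *b* the Korean and Taiwanese subjects reported as detected below 25, Overall at common 15 lies between planned − *b*/180 and planned. The value cannot be pinned down, because those results carry no number. The range can be read off the tables: *b* is the detected-below-LLOQ count for Overall minus that for China.

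**4. The China side has a bound too.** Tables 8.1, 11 and 12 show China separately. Let *m* be the Chinese subjects not below LLOQ at a visit. Anyone whom a 25 IU/mL limit would reclassify is among them, including missing visits set to failure, so the shift is at most *m*/180. If 94 of 100 Chinese subjects achieve SVR12 (assumed), *m* = 6 and the shift is at most 6/180 = 3.3 points. If all respond, it is zero. At early on-treatment visits *m* may be large and the bound loose. Listings 8.1 and 8.2 give the individual values and the virologic failures.

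**5. Means and proportions differ for a reason.** SAP 3.5 sets every value below LLOQ to 14 IU/mL in China and 24 IU/mL elsewhere. Two subjects with no detectable virus would differ by log10(24/14) = 0.23 log10 IU/mL, which biases pooled means for every suppressed subject. The category is misaligned only for subjects between 15 and 24.

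**6. A single band value need not decide SVR12.** The Week 12 visit falls on days 84 ± 5, that is 79 to 89 after the last dose. The analysis window runs from day 70 to day 146 (SAP Table 3-2), and SAP 3.7.3 takes the latest HCV RNA record in it. From day 89 there are 146 − 89 = 57 days in which a repeat below LLOQ would make the subject a responder. Protocol 6.4.9 provides for unscheduled visits to confirm virologic failure.

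**The case for a change.** The best case for a change is cost. Chinese values of 15 to 24 are already reported as numbers, so one supplementary Overall table at a common 25 IU/mL limit, with a count of such values per visit, would show whether the effect is nil. The reader would not have to search listings, and the SAP gives no reason for treating categories differently from means.

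Part of this stands. No planned table gives the count, the bound is loose early in treatment, and the reason in step 5 above has to be inferred.

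It does not carry the rest:

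- Reclassifying at 25 can only raise the Overall rates, so it adds a descriptive analysis that moves one way, in favour of the product.
- It does not produce a truly common limit, because two assay platforms remain.
- It cannot extend soundly to SVR24 or virologic outcome. Week 24 attendance (Protocol 3.4, 6.5.2) and on-treatment stopping (Protocol 3.5) were decided at each region's own LLOQ. Under SAP 3.6.1 a "success for SVR12 who have no further HCV RNA measurements collected will be counted as a success for SVR24", so reclassified subjects who were not brought back at Week 24 would be given SVR24 by imputation.
- One subject could be a non-responder in the China column and a responder in the supplementary Overall column.

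**Conclusion.** No change is needed. The mixed cut-off is real but openly stated, follows from an endpoint defined by the LLOQ and a protocol that permits both assays, and is confined to descriptive Overall columns. China is shown separately, and the SAP states that Korea and Taiwan were analysed under their own SAP and already reported. The primary test is unaffected, and the stricter limit applied to China cannot flatter its result.

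The size is 0.56 points of an Overall rate per Chinese subject with 15 to 24 IU/mL, downward against a common 25 IU/mL limit, and capped by the Chinese subjects not below LLOQ. This rests on the planned 180 per treatment-history group; by-visit denominators may be smaller, since on-treatment values after early discontinuation stay missing. The number of subjects in the band is unknown and may be zero.

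A footnote that the Overall proportions use region-specific LLOQs would be a courtesy in reporting, and analysts can add one without amending the plan.
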